9.7 Sample Collection and Processing

9.7.1 Blood Sample Collection

In each period :

- a total of 17 blood samples will be drawn from each subject for PK analyses. Blood samples will be collected prior to drug administration and 0.133, 0.25, 0.5, 1, 1.5, 2, 3, 4, 5, 6, 8, 10, 12, 16, 24, and 32 hours post-dose (3 mL for each sampling time). The time tolerance window for blood sample collection during the confinement period will be ± 1 minute for all samples collected before 8 hours post-dose and ± 3 minutes for subsequent samples. Sample collections done outside the pre-defined time windows will not be considered as protocol deviations since actual post-dose sampling times will be used for PK and statistical analyses. Unless otherwise specified or for subject safety, when blood draws and other procedures coincide, blood draws will have precedence. A saline intravenous catheter will be used for blood collection to avoid multiple skin punctures, when appropriate. Otherwise, blood samples will be collected by direct venipuncture.
- a total of 5 additional blood samples (for plasma and buffycoats) will be collected for potential RNA Seq analysis, iduronidase activity, and mRNA frataxin: pre-dose, and 3, 6, 12, and 24 hours post-dose (10 mL for each sampling time).

For study Part 1 only, PBMC will be isolated, from at most (maximum) 10 subjects at the following timepoints (16 mL for each sampling time):

- Period 1: pre-dose, 3, and 24 hours post dose;
- Period 2: 3, 6, and 24 hours post dose;
- Period 3: 3, 6, and 24 hours post dose.

PBMC will be isolated as per the Project Specific Procedure (PSP).

The total volume of blood including that collected for eligibility and safety purposes should not exceed 733 mL for the whole study (605 mL for subjects participating in study Part I only).

9.7.2 Urine Sample Collection for PK analysis

In study Part 1, urine will be collected for quantitation for PK analysis. Urine samples will be collected at 6 times or time intervals: spot pre-dose (within 2 hours before dosing), 0-4 hours, 4-8 hours, 8-12 hours, 12-24 hours, and 24-32 hours post-dose.

If a subject cannot void his or her bladder within 30 minutes before dosing, a sample from earlier that morning may be used as the pre-dose sample. Voids that occur within the time interval will

be pooled, and subjects will be asked to void their bladder within 10 minutes before the end of each collection interval, so that each new interval will begin with an empty bladder. Any urine voided by subjects at the intersection (within 10* minutes) of two intervals will be included in the earlier sample. Any urine voided by subjects but not collected will be documented.

**For Day 2 (24 hours post-dose) urine collection, subjects will be asked to void their bladder within 15 minutes before the end of the collection interval (12-24 hours).

Plasma and urine samples will be collected and processed as per the Analytical Methodology Information Sheet.

Since resveratrol is sensitive to light, blood and urine collection tubes will be protected from light, sample processing will be performed under sodium lamp, and urine and plasma samples will be transferred into amber vials.

Other investigations may be performed using remaining samples already collected.

9.8 Subject Monitoring

Subjects will be monitored throughout the study by the clinical staff for AEs. In each period, the Investigator or designee will be on site for drug administration and until 2 hours (study Part 1) and until 4 hours (study Part 2) post-dose, and available on call for the remainder of the study. If necessary, the Investigator or designee at the clinical site or a healthcare professional in a nearby hospital will administer treatment for any AE(s). A crash cart or emergency bag containing the necessary rescue material and appropriate medications will be available in the clinic to allow rapid intervention in case of emergency.

Safety parameters, including laboratory results and ECG, will be assessed by the Investigator or designee, using the clinical site's criteria for biomedical laboratory and ECG acceptance ranges as suggested guidelines in making the medical assessment.

Scheduled safety measurements will be repeated according to the clinical site SOPs or upon request from the Investigator or designee. Any abnormal repeated measurement will be evaluated by the Investigator or designee and repeated if judged necessary. Further action may be taken upon the Investigator or designee's request.

Subjects will be advised to notify their health care professional(s) (e.g. physician, dentist, and/or pharmacist) that they are participating in a clinical research study on a drug called resveratrol before taking any medicines or undergoing any medical procedure.

9.8.1 Vital Signs

Blood pressure, respiratory rate, oral temperature, and heart rate will be measured in a sitting position (except for safety reasons) at screening and study exit.

9.8.2 ECG

Supine ECG will be performed at screening and study exit.

9.8.3 Physical Examination

A physical examination will be performed at screening.

9.8.4 Cotinine, Drug, and Alcohol Screen

A urine drug screen (amphetamines, methamphetamines, barbiturates, benzodiazepines, tetrahydrocannabinol, cocaine, opiates, PCP, MDMA, methadone) and a urine cotinine test will be performed at screening. A urine drug screen, a urine cotinine test, and an alcohol breath test will be performed before dosing at check-in of each period.

9.8.5 Pregnancy Test

A urine pregnancy test will be performed at screening and at study exit, and a serum pregnancy test will be performed at check-in of each period.

9.8.6 Laboratory Assessments

9.8.6.1 RNA-Seq Analysis, Iduronidase, mRNA Frataxin, and Other Possible Tests

Potential RNA-Seq analysis will be performed before dosing and 3, 6, 12, and 24 hours post-dose in each period. Details for this analysis will be included in a separate protocol. Other investigational tests such as iduronidase activity measurement and mRNA frataxin may be performed by an external laboratory. Details of this additional laboratory work will be available in a separate protocol.

9.8.6.2 PBMC Isolation

PBMC will be isolated, from at most (maximum) 10 subjects on Days 1-2 in study Part 1.

9.8.6.3 Biochemistry

Biochemistry will be performed at screening and study exit. The following will be assessed: albumin, alkaline phosphatase, AST, ALT, urea, calcium, chloride, glucose, phosphorus, potassium, creatinine, sodium, total bilirubin, and total protein.

9.8.6.4 Serology

Serology will be performed at screening. The following will be assessed: HIV antigen and antibody, hepatitis B surface antigen (HBsAg), and hepatitis C virus (HCV) antibody.

9.8.6.5 Hematology

Hematology will be performed at screening, at check-in of **Period 3 (study Part 1) and of study Part 2 (Period 4)**, and at study exit. The following will be assessed: complete blood count with differential, hemoglobin, and hematocrit.

9.8.6.6 Coagulation

Coagulation tests will be performed at screening. The following will be assessed: prothrombin time/international normalized ratio (PT/INR) and activated partial thromboplastin time (aPTT).

9.8.6.7 Urinalysis

Urinalysis will be performed at screening and at study exit. The following will be assessed: macroscopic examination, pH, specific gravity, protein, glucose, ketones, bilirubin, occult blood, nitrite, urobilinogen, and leukocytes. Unless otherwise specified, microscopic examination will be performed according to internal procedures.

9.9 Study Exit Procedures

Hematology, biochemistry, urinalysis, urine pregnancy test, vital signs (blood pressure, respiratory rate, heart rate, and oral temperature), ECG, and AE monitoring will be performed on the last study day. For subjects who are not included in study Part 2, study exit procedures will be completed after the last blood draw of Period 3 (after 32 hours post-dose on Day 2). For subjects who are included in both study parts, study exit procedures will be completed after the last blood draw of Period 4 (after 32 hours post-dose on Day 2). If not possible, all efforts will be made to complete study exit procedures within 14 days after the last participation of the subject in the study.

9.10 Data Collection and Evaluation

Subjects' personal information will be stored in an electronic data capture (EDC) system (Initiator™ or Alphadas®). All clinical raw data will be recorded promptly, accurately, and legibly; either directly into the EDC system as e-source data or indelibly on paper (e.g., ECG readings or raw data sheets when electronic data capture is not possible). A detailed list of the type (electronic or paper) and location for all source data will be included in the Trial Master File. When recorded electronically, Case Report Forms will be electronically generated afterwards. All raw data will be conserved in order to maintain data integrity. The Investigator and/or the clinical staff have the responsibility of ensuring the completeness and accuracy of the clinical data. Initiator™ and Alphadas® are validated and are Code of Federal Regulations (CFR) part 11 compliant applications.

9.11 Subject Withdrawal and Replacement

Subjects will be advised that they are free to withdraw from the study at any time. Over the course of the study, the Sponsor and the Investigator or designee may withdraw any subject from the study for one of the reasons described below; subject withdrawal will be done in accordance with the clinical site's SOP:

- safety reason;
- non-compliance with protocol requirements;
- significant protocol deviation;
- positive cotinine, alcohol, drug, or pregnancy test;
- vomiting within 3 hours (study Part 1) and 7 hours (study Part 2) after dosing.

Subjects excluded from dosing in one period as per criteria listed above, may be invited to participate in subsequent periods of the study if deemed appropriate by the Investigator and appropriate from a statistical standpoint (i.e. would permit adequate statistical comparison). However, subjects with positive cotinine, alcohol, drug, or pregnancy test will be definitively withdrawn from the study. Hematology results will be reviewed by the Investigator or designee prior to dosing in Period 3 (study Part 1) and in Period 4 (study Part 2). Subjects will be

withdrawn from the study if it is deemed that the subject's safety may be at risk on the basis of these test results. Subjects who withdraw or are withdrawn from study Part 1 after dosing, for reasons other than safety and tolerability, may be replaced after consultation between the Safety Committee members and the DSMB members in order to assure initiating study Part 2 with 16 subjects. Such replacement resulting in dosing more subjects than planned in this protocol would be documented in a protocol amendment.

Subjects who withdraw or are withdrawn will be asked to remain at the clinic until the Investigator or a designee agrees that the subject is fine and can be discharged. As soon as subject withdrawal is confirmed, blood sampling will be stopped. A PK blood draw may be collected at the time of withdrawal if deemed required by the Investigator. Study exit procedures will be performed at the time of withdrawal from the study or as soon as possible thereafter.

9.12 Adverse Events

9.12.1 Recording of Adverse Events

AEs will be recorded and evaluated for their seriousness, severity, and relationship to the study medication. AEs will be collected and documented during the course of the study and until 4 days following the last study drug administration, if reported. AEs will be followed-up until complete resolution, or until the Investigator judges it to be safe to discontinue follow-up. The relationship to the study medication will be classified according to the clinical site SOPs.

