	
b) over-the-counter products and natural health products (including herbal remedies, homeopathic and traditional medicines, probiotics, food supplements such as vitamins, minerals, amino acids, essential fatty acids, and protein supplements used in sports) within 14 days prior to the first dosing, with the exception of the occasional use of acetaminophen (up to 2 g daily);
 
c) use of any drugs known to induce or inhibit hepatic drug metabolism, including St. John's wort, within 30 days prior to the first study drug administration;
 
d) depot injection or an implant of any drug within 3 months prior to the first dosing.
 
12) Donation of plasma within 7 days prior to dosing. Donation or loss of blood (excluding volume drawn at screening) of 50 mL to 499 mL of blood within 30 days, or more than 499 mL within 56 days prior to the first dosing.
 
13) Any reason which, in the opinion of the Investigator, would prevent the subject from participating in the study.

Screening Procedures:	Demographic data, medical and medication histories, physical examination, body measurements, electrocardiogram (ECG), vital signs (blood pressure, heart rate, respiratory rate, and oral temperature), hematology, biochemistry, coagulation, serology (human immunodeficiency virus [HIV], hepatitis B and C tests), urinalysis, urine cotinine test, urine pregnancy test, and urine drug screen.
Confinements, Visits, and Washout:	
For each period, subjects will be confined from Day -1 until after the 32-hour post-dose blood draw.
 
There will be a washout period of 14 days or more between each study drug administration.

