9.2 Confinements, Visits, and Washout

For each period, subjects will be confined from Day -1 until after the 32-hour post-dose blood draw.

There will be a washout of 14 days or more between doses. The washout period may be increased for logistical considerations. Participation of each subject in this study should last approximately 1 month (for subjects participating in study Part 1 only) and 1.5 months (for subjects participating in both study parts).

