9.5 Drug Administration

Study medication will be administered to each subject with approximately 240 mL of water and a hand and mouth check will be performed to ensure consumption of the medication. Additional water may be provided if needed.

Study Part 1 (Periods 1, 2, and 3): All subjects will be sequentially dosed in an ascending manner with at least 14 days between the last dosing and the subsequent nominal dose level which will be calculated based on observed safety, tolerability, and PK results. Subjects will receive a single oral dose of JOTROL gelcaps under fasting conditions using the following nominal dosage levels:

Study period	Planned dose levels of JOTROL
1	200 mg (given as 2 x 100 mg gelcaps), total dose of resveratrol: 200 mg
2	500 mg (given as 5 x 100 mg gelcaps), total dose of resveratrol: 500 mg
3	1000 mg (as 10 x 100 mg gelcaps), total dose of resveratrol: 1000 mg

For Periods 2 and 3, JOTROL's doses to be administered will be reassessed when safety, tolerability, and PK data analysis are available. Adjustment to the currently outlined doses and/or dosing regimen may be necessary, but the dose to be administered in Period 2 or 3 will not exceed the one currently outlined in the protocol.

Time of dosing will be set equal to the time when the first gelcap is administered to the subject. The complete dosing procedure must be completed within 3 minutes.

Following completion of each dose level, PK, safety, tolerability data will be evaluated by a Safety Committee **and a DSMB** before proceeding to the next dose.

The same JOTROL dose will be administered in Periods 3 and 4.

Study Part 2 (Period 4): Only 16 subjects who completed study Part 1 will receive the highest dose of JOTROL tested during study Part 1, as a single oral dose of JOTROL gelcaps under fed conditions. In order to minimize potential PK variability, elderly (more than 65 years old subjects) will be not included in study Part 2. However, depending on safety and tolerability as well as on available PK data from Part 1 (in order to keep AUC exposures lower than 2.1 $\mu\text{g}\cdot\text{hr}/\text{mL}$, as specified in section 7.2.), the dose to be used during study Part 2 may be reduced.

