### 9.2 Adverse Events

AEs will be recorded and evaluated for their seriousness, severity, and relationship to the study medication. AEs will be collected and documented during the course of the study and until 4 days following the last study drug administration, if reported. AEs will be followed-up until complete resolution, or until the Investigator judges it to be safe to discontinue follow-up. The relationship to the study medication will be classified according to the clinical site SOPs.

Treatment-emergent AEs and non-TEAEs (those occurring prior to administration of study medication or that first occurred prior to study drug administration and did not worsen in frequency or severity) will be listed. TEAEs will be defined as AEs that occur on or after the date and time of study drug administration, or those that first occur pre-dose but worsen by increase in occurrence or severity after study drug administration. AEs will also be documented if reported.

The incidence of TEAEs will be summarized using the safety population. The MedDRA® dictionary Version 23.1 will be used to classify all AEs reported during the study by SOC and PT.

Incidence of subjects who experienced TEAEs will be presented by treatment and overall, SOC, PT, by Investigator-assessed relationship and also by severity. Each subject may only contribute once to each of the incidence rates, for a TEAE following a given treatment, regardless of the number of occurrences; the highest severity or highest relationship will be presented, as appropriate. In each table, SOC will be presented in descending order of overall incidence rate in terms of frequency of subjects and then in frequency of events (alphabetical order will be used in case of equal rates). For each SOC, PT will be presented the same way.

Incidence of TEAEs (number of events) will also be presented by period(dose) and overall, by SOC, and PT, by Investigator-assessed relationship and severity.

Frequency of subjects experiencing Serious Treatment Emergent Adverse Events and Suspected Unexpected Serious Adverse Drug Reactions; and the number of events would be also summarized per treatment and overall. Also, these events and Serious Adverse Events (SAEs) will be listed per subject.

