**12. Handling of Missing Data**

For safety,

- If an AE is recorded with an onset date corresponding to a dosing day, but the time is missing, then the AE will be assigned to the treatment phase planned treatment with a dosing planned that day.
- If an AE is recorded with an onset date that does not correspond to a dosing day, but the time is missing, then the AE will be assigned to the treatment phase planned treatment that covers the AE onset day.
- If an AE is recorded with an onset date where day and time are both missing, then the AE allocation to a treatment phase planned treatment will be done on a case by case basis considering available information (e.g. AE onset date, AE end date, AE comments, subject disposition).

For PK, only observed data will be used in the data analysis except for concentration values BLQ as described in Section 10.1. No attempt will be made to extrapolate or interpolate estimates for missing data.

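### By-treatment TEAE incidence rests on windows of at least 14 days after non-final doses but nominally 4 days after the last dose, which flatters Treatment D and, to a lesser degree, Treatment C

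*Protocol*

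**What the plan says.** **Collection period.** Protocol 9.12.1 ends collection of new AEs "until 4 days following the last study drug administration, if reported". SAP 9.2 repeats the rule: "AEs will be collected and documented during the course of the study and until 4 days following the last study drug administration, if reported".

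**Dose spacing.** Protocol 9.2 states: "There will be a washout of 14 days or more between doses". The Synopsis agrees, and 9.2 allows a longer interval for logistical reasons.

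**Definition and attribution.** In SAP 9.2 a TEAE starts at dosing; no end to the at-risk period is given. SAP 5 tabulates TEAEs by treatment phase, but no section says when a phase ends. The nearest rule is in SAP 12. For an AE with a missing time whose onset is not on a dosing day, "the AE will be assigned to the treatment phase planned treatment that covers the AE onset day". Phases therefore run past the day of dosing.

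**Output.** SAP 9.2: "Incidence of subjects who experienced TEAEs will be presented by treatment and overall", with breakdowns by system organ class, preferred term, relationship and severity. There is no common window, no adjustment for time at risk and no TEAE table by age.

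**Whose last dose is when.** Part 1 has 24 subjects and 16 continue to Part 2, taken in order of enrolment (Protocol 8.1). Protocol 9.5 adds that "elderly (more than 65 years old subjects) will be not included in study Part 2".

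**Contact.** In every period subjects leave after the 32-hour draw. The Schedule of Events places an AE review at each Day -1 check-in. Exit procedures, which include AE monitoring, are due after the 32-hour draw of the last period, or within 14 days if that is not possible (Protocol 9.9).

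**The concern.** A crude proportion of subjects with at least one event rises with the length of time over which events are counted. Treatments A and B are each followed by another dose, so events count against them for 14 days or more. Treatment D is always a subject's last dose, so its window closes nominally at day 4. Treatment C mixes the two. The table then sets the four proportions side by side.

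The clearest case is fed against fasted. The same 16 subjects, planned to receive the same dose, have at least 14 days after Period 3 and 4 days after Period 4. Treatment D supplies the only fed tolerability data in the study. A reader of the clinical study report could take a lower all-cause TEAE proportion on D as good tolerability with food when it reflects only a shorter count.

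**Working it through.** **Inputs from the documents.** 24 subjects on A, B and C and 16 on D (Protocol 8.1), so 24 − 16 = 8 have Period 3 as their last dose. Minimum interval between doses 14 days (Protocol 9.2). Collection after the last dose 4 days (Protocol 9.12.1). Published resveratrol half-life 9.2 h (Protocol 4.3.2).

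**Assumed.** The documents give no background AE rate. I take a probability m of at least one background event over 14 days, from 5% to 50%, with constant hazard and equal detection on each day.

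**Step 1: reproduce the plan's figure.** The plan states no AE-rate calculation. The one stated figure that depends on the 14-day interval is participation length, "approximately 1 month (for subjects participating in study Part 1 only) and 1.5 months (for subjects participating in both study parts". Counting from Day -1 of Period 1 to Day 2 of the last period gives 31 days (31/30.4 = 1.02 months) for Part 1 only and 45 days (45/30.4 = 1.48 months) for both parts. The stated lengths reproduce, so a window of about 14 days after non-final doses is what the plan intends.

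**Step 2: minimum collection time per treatment.**

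| Treatment | Subject-days | Days per subject |
|---|---|---|
| A | 24 × 14 = 336 | 14.0 |
| B | 24 × 14 = 336 | 14.0 |
| C | 16 × 14 + 8 × 4 = 256 | 10.7 |
| D | 16 × 4 = 64 | 4.0 |

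The ratio of A or B to D is 14/4 = 3.5.

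**Step 3: displayed incidence with no true difference.** With daily hazard λ = −ln(1 − m)/14, the 4-day incidence is p4 = 1 − exp(−4λ). A and B show m, D shows p4, and C shows (16m + 8·p4)/24.

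| Assumed m | A and B | C | D | D/A |
|---|---|---|---|---|
| 5% | 5.0% | 3.8% | 1.5% | 0.29 |
| 10% | 10.0% | 7.7% | 3.0% | 0.30 |
| 30% | 30.0% | 23.2% | 9.7% | 0.32 |
| 50% | 50.0% | 39.3% | 18.0% | 0.36 |

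In the 16 subjects who take both C and D, the expected number with an event is 16 × 0.10 = 1.6 fasted against 0.47 fed at m = 10%, and 16 × 0.30 = 4.8 against 1.55 at m = 30%.

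**Step 4: add an acute drug effect, equal on all treatments.** Assume 20% of subjects have a drug-related event within 4 days, with m = 10%. A and B show 1 − 0.8 × 0.9 = 28.0%. D shows 1 − 0.8 × (1 − 0.0297) = 22.4%. C shows (16 × 28.0 + 8 × 22.4)/24 = 26.1%. The distortion shrinks in relative terms but keeps its direction.

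**Step 5: what lies beyond day 4.** At 9.2 h, 96 h is 96/9.2 = 10.4 half-lives, which leaves about 0.07% of drug. At the longest mean half-life in Protocol Table 1 (11.5 h, a metabolite), it is 96/11.5 = 8.3 half-lives and about 0.3%. These are published resveratrol data, not JOTROL data.

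**Step 6: common 4-day window.** Subject-days become 96, 96, 96 and 64, or 4.0 per subject on every treatment. The step 3 incidence is then p4 throughout, and the step 4 incidence is 22.4% throughout.

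**The case against.** **No drug-related events are shown to be missed.** A reader might infer that drug-related TEAEs on the fed treatment are undercounted. The documents do not support that. At the half-lives in step 5, acute drug effects should fall mostly within 4 days. The gap is better described as extra background events on A and B. This objection stands, and it limits the point to relative, all-cause incidence.

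**Older subjects.** A reader might also infer that TEAE rates in older subjects at the top dose are understated. No such rate is planned: age group appears only among the demographics (SAP 8.3). The short Period 3 window applies to all 8 subjects who stop after Part 1. That includes anyone over 65, whose number is not fixed, and also any younger subject not reached in enrolment order. The affected outputs are Treatments C and D.

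**Other outputs help.** TEAEs are also tabulated by relationship and severity, and background events should tend to be judged unrelated. That helps, but attribution in an open-label study is imperfect and the all-cause table is still produced.

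**The table is descriptive.** Both objectives are pharmacokinetic, no inferential safety analysis is planned, escalation rests on committee review and event-based stopping rules, and treatment is fully confounded with period. All true, and a reason to keep the point in proportion. Confounding that the design cannot remove is no reason to keep a bias that the SAP can.

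**The windows are less sharp than 14 and 4.** Exit with AE monitoring may slip by up to 14 days, and events between discharge and the next check-in are partly recalled. The first makes the last window variable between subjects without equalising it. The second suggests that the effective gap may be smaller than step 3 shows.

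**Conclusion.** The concern holds in a limited form. As written, SAP 9.2 reports crude TEAE incidence by treatment over minimum windows of 14.0, 14.0, 10.7 and 4.0 days per subject. With no true difference, the all-cause tables favour D, and less strongly C, over A and B. Under constant hazard and an assumed 14-day background of 5% to 50%, D would show 0.29 to 0.36 of the A or B figure. The window counts follow from the documents; the incidence figures rest on the assumed rate and on even detection.

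The effect is on relative, all-cause incidence. It is not evidence that drug-related events go uncounted, and it is not a finding about older subjects as a group. It does not touch the pharmacokinetic objectives or dose escalation. It is worth correcting because the bias is predictable, is largest in the fed against fasted comparison, and can be removed at the analysis stage.

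**What to change.** **SAP 9.2.** Base the by-treatment TEAE incidence tables on one onset window for all four treatments, from dosing to 4 days post-dose. List AEs with later onset separately by last treatment received, and keep them in the overall count. State in SAP 5 or 9.2 when a treatment phase ends, so that attribution does not rest on the missing-time rule in SAP 12.

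**Alternative.** Report rates per subject-day at risk. This is my second choice, because acute events cluster early and long windows dilute them. In the step 4 example, equal true risk would display as 28.0/14 = 2.0 subjects with an event per 100 subject-days on A and B, against 22.4/4 = 5.6 on D.

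**Cost.** SAP wording only, using onset dates already collected. Events with onset after day 4 leave the comparative table but remain listed. A residual difference stays: between discharge and day 4 after the last dose, capture depends on the subject reporting, whereas after other doses AEs are reviewed at the next check-in. A scheduled contact at day 4 would address that, but it is optional and the correction does not depend on it.
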